2.4 Treatments (study treatment, rescue medication, concomitant therapies, compliance)

2.4.1 Study treatment / compliance

Summary of treatment exposure and compliance by cohort and overall will be presented up to week 24 for Core phase analysis, from E0 to E4 for extension phase and overall from visit 3 to E4 on the Safety set.

Duration of exposure

The exposure to investigational drug (number of doses) and duration of exposure (days) will be summarized by cohort and overall.

Duration of exposure will be defined as the time from first dose of study treatment to the last dose of study treatment for all patients.

Compliance

Compliance will be calculated based on documented study treatment administration details and displayed by cohort and overall as well as study period (i.e. induction, maintenance and extension). Total actual dose will be compared with the total dose patients should take as per protocol and derived compliance will be summarized.

Total actual dose for Core phase will be derived as

Total actual dose = Actual amount of dose of Secukinumab 300 mg upto week $24 \times$ Frequency of dose upto week 24.

The treatment compliance will be calculated as

Treatment compliance (%) = $\frac{\text{the actual number of injections received by a patient}}{\text{the scheduled number of injections}} \times 100.$

Compliance is expected to be 100%, unless temporary interruption is needed for safety reasons.

Similar definition will also hold for extension and overall duration.

Drug interruptions

The number and percentage of patients with study drug interruptions and the reasons that led to the interruption will be summarized by cohort and overall as well as per study period (i.e. induction, maintenance and extension) on the Safety set.

2.4.2 Prior, concomitant and post therapies

The use of rescue medication, concomitant medications and significant non-drug therapies will be summarized by Anatomic Therapeutic Chemical (ATC) class – level 2 and PT, by cohort and overall on the Safety set.

Prior and concomitant therapies

Any medications entered will be coded using the WHODrl dictionary version WHODD 1 or latest available. Concomitant medications will be summarized in separate tables by cohorts and overall on the Safety set. Medications will be presented in alphabetical order, by Anatomical Therapeutic Classification (ATC) codes level 2 and PT, grouped by anatomical main group. Tables will show the overall number and percentage of patients receiving at least one treatment of a particular ATC code and at least one treatment in a particular anatomical main group.

Previous psoriasis therapies will also be summarized by cohort including p-values which will be calculated using logistic regression, adjusted by age (tertiles), sex and number of comorbidities.

Additionally, the number of patients naive, number of patients with previous systemic therapy, and number of patients with previous biologic therapy will also be summarized. The categories "Topical", "Phototherapy", "Missing" will NOT be counted to derive the Naïve group.

Moreover the total number of previous psoriasis therapies will be analyzed similar to total number of comorbidities (General and PsA) and p-values (using same model and covariates) will be reported for comparison of cohorts.

Concomitant medication will be identified by comparing recorded or imputed start and end dates of medication taken to the reference start date.

Rescue medication

Rescue medication is defined as medication used to control symptoms that are not adequately controlled on study treatment.

The treatments 'METILPREDNISOLONE', 'ACITRETINE', 'ELOCON CREAM' with reasons in 'WORSENING OF PSORIASIS', 'ERYTHEMA AND DESQUAMATION IN PSORIASIS AREA', 'ERYTHEMATOUS DESQUAMATIVE LESIONS ON THE PALMS OF HANDS' will be considered as rescue medication for this study.

Rescue medication will be summarized by Anatomic Therapeutic Chemical (ATC) class and PT, by study phase and by cohort and overall on the Safety set.

Procedures and significant non-drug therapies

Procedures and significant non-drug therapies will be summarized by system organ class (SOC) and preferred term (PT), by cohort and overall on the Safety set.

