5.5.6 Rescue medication

The investigator may prescribe any medications and/or supportive care during the study based on clinical needs. Use of rescue medication must be recorded on the Concomitant medications/Significant non-drug therapies/Dose Administration Record in the Electronic Case Report Form (eCRF).

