5.5.8 Prohibited Treatment

Use of the treatments displayed in [Table 5-1](#) is NOT allowed after screening.

If a prohibited treatment listed in [Table 5-1](#) is used during the study, the patient must discontinue use of the prohibited treatment if he/she wishes to continue in the study. At the discretion of the investigator, if the patient's use of a prohibited treatment presents undue safety risk for the patient, he/she should be discontinued from study treatment as per [Section 5.5.9](#). If the patient receives a live virus vaccination during the study, he/she must discontinue study treatment and enter the post-treatment follow up period.

Table 5-1: Prohibited treatment

Prohibited treatments	Washout period (before day 1)
Secukinumab or any other biologic drug directly targeting IL-17 or the IL-17 receptor	No prior use allowed
Ustekinumab	No prior use allowed
Alefacept, briakinumab, efalizumab	6 months
Biological immunomodulating agents other than the above:	
Etarnecept	3 weeks
Adalimumab	6 weeks
Infliximab	12 weeks
Golimumab	8 weeks
Other systemic immunomodulating treatments [e.g., MTX, cyclosporine A, corticosteroids (oral, i.v., intramuscular, s.c., intra-articular, transdermal), cyclophosphamide]	4 weeks
Other systemic psoriasis treatments (e.g. retinoid, fumarates)	4 weeks
Photo chemotherapy (e.g. PUVA)	4 weeks
Phototherapy (e.g., UVA, UVB)	2 weeks
Topical treatment that is likely to impact signs and symptoms of psoriasis (e.g. vitamin D analogues, pimecrolimus, retinoids, salicylvaseline, salicylic acid, lactic acid, tacrolimus, tar, urea alpha-hydroxy or fruit acids)	2 weeks

Live virus vaccinations	6 weeks
Any investigational treatment or participation in any interventional trial	4 weeks or 5 half-lives (whichever is longer)
Prohibited regimen of Topical Corticosteroids (TCS):	
TCS higher than moderate potency on any body location	2 weeks
TCS mild to moderate potency on any body location other than the face, scalp and or genitoanal area	2 weeks
TCS mild to moderate potency on the face, scalp and or genitoanal area	1 day

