• For the subjects who did not enter Extension Phase, all events/medications belongs to Core Phase

- · If event/medications start date is on or before visit date of E0, then APERIOD=Core Phase
- If event/medications start date is after visit date of E0, then APERIOD=Extension Phase.

For Planned data (i.e., Visit wise, all safety and efficacy) will be derived as below:

- · Visits before E0 will belong to Core Phase
- · Visits on or after E0 will belong to Extension Phase

Basically reporting will be done for visit assessment data in extension phase which is collected on or after ICF is signed for extension phase.

The above rules are irrespective of whether V12 visit date and E0 visit date are same or different.

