The cost for all items of assistance provided to the patient and included into the economic evaluation will be calculated according to price (such as for drugs) or tariffs (such as for tests).

For the costs attribution, since costs will not be collected in the CRF, an estimate for the following health services will be reported:

- drug treatment (ie. rescue medication)
- diagnostic services

In particular, for rescue medications (methotrexate, corticosteroids), cost will be assessed according to the dosage reported in the Patient Information Leaflets (PILs), considering an average price at the time of purchase.

Specialist services (Chest X-Ray, ECG, clinical chemistry tests, hematology tests, urinalysis) costs will be derived from regional tariffs and provided in a separate excel file (modified from http://salute.regione.emilia-romagna.it/documentazione/nomenclatore-tariffario-rer/nomenclatore_tariffario.xls/view); estimate costs for one month of rescue treatment will be reported in the same excel file.

Even though cost data are typically non-normally distributed (truncated at zero and positively skewed, reflecting the fact that some patients incur high costs), the arithmetic mean and standard deviation are the most informative measures in cost analysis.

These parametric methods are known to be fairly robust to non-normality, especially if the sample size is large, however robustness for a particular data set is difficult to judge.

All analyses will be performed considered the whole sample as denominator (ie. including those patients with a value equal to zero in a specific resource or in a specific cost item); for

example, for the number (and cost) of dermatological visits, the mean will be calculated as the sum of the dermatological visits in the whole sample divided by the number of subjects of the whole sample.

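### Rescue medication is identified by a fixed list of verbatim entries that disagrees with the SAP's own cost list, and rescue carried over from the core phase is missing from the extension column

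*SAP*

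**What the plan says.** **Purpose.** SAP 2.4.2 opens with a general definition: "Rescue medication is defined as medication used to control symptoms that are not adequately controlled on study treatment".

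**Operational list.** The next sentence names three drug entries and the first of three reasons: "The treatments 'METILPREDNISOLONE', 'ACITRETINE', 'ELOCON CREAM' with reasons in 'WORSENING OF PSORIASIS". It ends with the third reason and the instruction that such records count: "ERYTHEMATOUS DESQUAMATIVE LESIONS ON THE PALMS OF HANDS' will be considered as rescue medication for this study". Nothing is said about other drugs, spellings or reasons.

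**Table.** The output is set in the same section: "Rescue medication will be summarized by Anatomic Therapeutic Chemical (ATC) class and PT, by study phase and by cohort and overall on the Safety set".

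**Phase.** SAP 2.1.1.5 assigns concomitant medications by start date only. A start on or before E0 gives "visit date of E0, then APERIOD=Core Phase"; a later start gives the extension phase. The end date plays no part. SAP 1.1 sets the denominator for every extension percentage as the number of patients who entered the extension.

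**Costs.** SAP 2.11, under resource utilization, uses another list: "for rescue medications (methotrexate, corticosteroids), cost will be assessed" from package-leaflet dosage and average price.

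**Protocol.** Section 5.5.6 sets no drug list: "The investigator may prescribe any medications and/or supportive care during the study based on clinical needs". Section 5.5.8 begins "Use of the treatments displayed in" Table 5-1 and goes on to bar them after screening. That table includes systemic corticosteroids, retinoids, methotrexate and certain regimens of topical corticosteroid.

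**The concern.** The rescue table is the one planned summary that shows, by phase and cohort, how often patients needed other treatment for psoriasis while on secukinumab. A reader will use it when judging how far a maintained response can be credited to the drug, and sustained response to week 72 is a stated aim of the extension.

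Three features work against that use. The list is narrower than the definition that precedes it. The SAP gives two incompatible accounts of what rescue is. The start-date rule leaves out of the extension column a patient who entered the extension already on rescue and stayed on it. The cost list also feeds the secondary objective on resource use, so drug costs and rescue counts would describe different sets of records.

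**Working it through.** The plan gives no figure to reproduce. The check sets the rules side by side and then applies them to invented records.

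**Step 1: the two lists.**

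| Drug | Rescue in SAP 2.4.2 | Rescue in SAP 2.11 |
|---|---|---|
| Methotrexate | no | yes |
| Acitretin | yes | no |
| Methylprednisolone | yes, with a listed reason | yes, if read as a corticosteroid |
| Elocon cream | yes, with a listed reason | yes, if read as a corticosteroid |

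The first two rows conflict on any reading.

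**Step 2: the rules applied.** E0 is placed on day 168, the scheduled day for week 24 in SAP Table 2.1. The records are made up and show how the rules behave, not how often each case occurs.

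| # | Record | Days | Rescue under 2.4.2 | Phase under 2.1.1.5 | Taken after E0 |
|---|---|---|---|---|---|
| 1 | Elocon cream, listed reason | 150–260 | yes | Core | yes |
| 2 | Elocon cream, listed reason | 168–300 | yes | Core | yes |
| 3 | Elocon cream, listed reason | 169–300 | yes | Extension | yes |
| 4 | Methotrexate, listed reason | 200–300 | no | Extension | yes |
| 5 | Methylprednisolone, spelled with an H, listed reason | 100–120 | no, on a literal match | Core | no |
| 6 | Elocon cream, reason given as psoriasis flare | 100–120 | no | Core | no |

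Records 1 to 4 are all treatment for psoriasis taken during the extension. The extension column of the rescue table would show only record 3. Records 2 and 3 differ by one day in start date and change column. Records 1 and 2 are not lost: they are shown under Core and overall.

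**Step 3: what one omitted patient does to the extension percentage.** The denominator is all extension entrants, planned at about 306. A carried-over patient is in the denominator but not the numerator, so each one lowers the percentage by 100 × 1/306 = 0.33 percentage points. The number of such patients is not in the documents, so no total follows.

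**Step 4: where the rescue flag goes.** The LOCF and non-responder rules in SAP 2.5.3 do not refer to rescue, nor does the primary comparison in SAP 2.5.2. In SAP 2.4.2 the flag feeds a descriptive Safety-set table. The separate SAP 2.11 list feeds the cost estimate.

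**The case against.** The case for leaving this alone has several parts.

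- **The list may be complete.** The Italianate spelling and the very specific palm-lesion reason look like entries copied from the database. If the list came from a full review of the records, nothing may have been missed. That is plausible, but the SAP does not say it, and it would not explain methotrexate in 2.11.
- **Unlisted rescue is still reported.** It appears in the concomitant medication tables. Deviation codes COMD17, COMD18 and COMD19, which SAP 2.3 lists under concomitant psoriasis medication, exclude patients from the per-protocol set used for supportive primary analyses. This stands in part: the planned concomitant medication tables are by ATC level 2, preferred term and cohort, without phase or reason. A corticosteroid for psoriasis cannot be told apart there from one given for something else.
- **Start-date allocation is a legitimate convention.** It keeps a record from appearing in two phases. That is true, but it suits a count of new starts better than a table read as use during a phase.
- **Long carry-over should be uncommon.** Entry to the extension requires PASI 75 at week 24, and the listed products are largely of types that Table 5-1 restricts. This limits the likely number. It does not exclude such patients, because entry carries no condition on rescue use.

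A reader might infer that rescue is undercounted, and most of all in the extension. The documents show that omission from a column is possible; they do not show that it happened or where it would be greatest. Nor is carried-over rescue uncounted: it is in the Core column and overall.

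**Conclusion.** The point holds as an inconsistency of definition and of phase allocation. SAP 2.4.2 states a purpose-based definition and then applies a narrower list with no rule for other entries. SAP 2.4.2 and 2.11 cannot both describe rescue in this trial. Rescue carried across E0 is absent from an extension percentage whose denominator includes the patient.

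The reach is limited to the descriptive rescue table and the resource-use costs. It would be wrong to conclude that the PASI 90 result is affected by this route, since no PASI 90 analysis uses the rescue flag. The number of patients affected cannot be computed from the documents; the 0.33-point figure is per patient and assumes the planned 306 enter the extension. The conclusion also assumes that the list is applied literally and that the start-date rule for medications governs the rescue table. The SAP wording supports both readings, though it does not say that only the listed entries qualify.

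**What to change.** 1. In SAP 2.4.2, keep the purpose-based definition and apply it through coded ATC class plus a recorded psoriasis indication. Have the resulting term list reviewed blind to Cw6 before database lock, and state that this was done. The verbatim entries can stay as examples.
2. Use that one list in both 2.4.2 and 2.11.
3. In SAP 2.1.1.5, count a medication in every phase that its start and end dates overlap, at least for the rescue table. A record may then appear in both phases, but once in the overall column; a footnote covers this.
4. Do not define rescue as the classes in Table 5-1. That would presuppose how the protocol sections below are to be reconciled.

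The cost is SAP wording, a small programming change and one blinded term review. ATC coding of medications is already planned; the blinded review is extra work, though short.

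Separately, the sponsor must reconcile three protocol sections. Section 5.5.6 permits any medication, 5.5.8 lets a patient continue if a prohibited treatment is stopped, and 5.5.9 requires study treatment to be discontinued when a prohibited treatment is used. As written, one record can be permitted rescue, a prohibited treatment and a ground for discontinuation. No view is taken here on which rule should prevail.

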2.5 Analysis of the primary objective

The primary objective of this study is to evaluate the clinical response in Cw6-negative and Cw6-positive patients treated with secukinumab 300 mg with respect to the Psoriasis Area Severity Index (PASI) 90 response rate after 16 weeks, and thereafter for up to 72 weeks.

2.5.1 Primary endpoint

The primary efficacy endpoint is proportion of patients with PASI 90 response after 16 weeks of treatment, defined as the achievement of \ge 90% improvement (reduction) in PASI score after 16 weeks of treatment compared to baseline, and thereafter for up to 72 weeks.

The primary analysis will be based on the ITT population.

2.5.2 Statistical hypothesis, model, and method of analysis

The proportion of patients who reach PASI 90 at 16 weeks will be presented with the one-tailed 97.5% confidence interval of the Cw6 positive (POS) – Cw6 negative (NEG) difference.

The null hypothesis:

H0: Cw6 POS - Cw6 NEG \ge 0.12: The difference in proportion of patients achieving PASI 90 response between the Cw6-positive cohort (Cw6 POS) and the Cw6-negative cohort (Cw6 NEG) is at least 12%.

The alternative hypothesis:

HA: Cw6 POS - Cw6 NEG < 0.12: The difference in the proportion of patients achieving PASI 90 response between the Cw6-positive cohort (Cw6 POS) and the Cw6-negative cohort (Cw6 NEG) is less than 12%.

The proportion of PASI 90 response by cohort as well as the difference between cohort together with 97.5% upper CI will be provided using Clopper Pearson CI method.

A logistic regression analysis model will also be fitted, considering age, geographical region (i.e. north vs south vs central), BMI categories (<25 vs >=25), waist circumference, smoking status (Yes vs No), metabolic syndrome (yes vs no), previous PsO therapy (naïve vs previous systemic therapy vs previous biologic therapy), PsA (yes vs no), age at diagnosis of psoriasis, TNF α -308 polymorphism, IGA mod 2011 (severe, moderate, mild) as strata factors.

Model selection:

If model does not converge due to particular covariate(/s), the corresponding covariate(/s) will be removed from the model using Stepwise selection method until model get converged.

Interpretation:

We can conclude that PASI 90 response in the Cw6-negative cohort is not less than 12% with respect to the Cw6-positive cohort if the upper bound of the 97.5 % CI of the difference (Cw6 POS - Cw6 NEG) is less than the non-inferiority margin of 12%.

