2.14 Interim analysis

No interim analysis is planned for this study.

3 Sample size calculation

The primary objective of this study is to evaluate the clinical response in PASI 90 at week 16 of Cw6-negative and Cw6-positive psoriatic patients. According to literature data, Cw6-positive patients will be about 60% of the entire psoriatic patient population.

From a previous study with ustekinumab (Talamonti et al. 2013) we can observe a difference in response to PASI 90 between Cw6-positive vs Cw6-negative patients of around 30%, in favor of Cw6-POS. Therefore, it is sensible to expect a response in the Cw6-negative cohort not less than 12 % respect to the Cw6-positive group. Further considerations are stated in the paragraph below.

Phase III data on secukinumab show a PASI 90 response at 16 weeks of 71%. Under the assumption that 60% of all the enrolled patient population is represented by Cw6-POS patients, we can reasonably assume to observe a proportion of patients with PASI 90 of 80% in the Cw6-POS cohort.

Under these assumptions, considering a one-side alpha level of 0.025 and a power of 80%, 365 patients (219 Cw6-POS and 146 Cw6-NEG) are sufficient to evaluate if the response in terms of PASI 90 in the Cw6-negative cohort is not less than 12% respect to the Cw6-positive cohort.

Considering a dropout rate at 16 weeks of 10% equally divided in the two studied cohorts, a total of 406 patients should be enrolled.

All calculations were done with NQuery 7.0.

A power analysis based on a different Cw6 patient distribution was made in order to facilitate patient enrollment without power-loss in the primary endpoint evaluation. Table 3-1 shows how the enrollment rate should be set free until the ratio between Cw6-POS and Cw6-NEG reaches the 1:1 rate-distribution, with a power of at least 80%.

In particular, the number of Cw6-POS evaluable patients will range from 219 to 182, whereas those in the Cw6-NEG cohort will range from 146 to 182.

Based on the table below, the enrollment in one of the two cohorts will be stopped when the target number is achieved (a maximum of 244 Cw6-POS patients will be allowed).

Table 3-1:Power analysis

Power	Ratio	Cw6	Cw6	Cw6	Cw6	Overall	Cw6	Cw6	

For business use only

		POS	POS	POS	POS		POS	POS
		%	%	Ν	Ν	Ν	%	%
80%	0.66	60%	40%	219	146	365	244	163
80%	0.70	59%	41%	215	150	365	239	167
80%	0.72	58%	42%	212	153	365	236	170
80%	0.75	57%	43%	209	156	365	233	174
81%	0.79	56%	44%	204	161	365	227	179

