5.4 Statistical models

5.4.1 Primary analysis

The SAS procedure PROC LOGISTIC, will be used to perform Logistic regression with the following sample SAS code:

PROC LOGISTIC DATA = \dots ;

CLASS usubjid acenter trtpn region smkst bmi .. / param=glm;

MODEL aval = trtpn region smkst bmi bl..;

LSMEANS trtpn / diff cl exp;

Ods output diffs=lsm_diff;

RUN;

In cases where separation is a concern, e.g. 0% response in one cohort, an exact logistic regression model will be applied. To ensure convergence, this model will not include any continuous covariates.

PROC LOGISTIC DATA = exactonly;

CLASS usubjid acenter trtpn region smkst bmi .. / param=glm;

MODEL aval = trtpn region smkst bmi bl..;

EXACT trtpn / estimate=both;

Ods output exactoddsratio=exactoddsratio;

RUN;

The SAS procedure PROC FREQ using Z-test with riskdiff option, will be used to derive Confidence intervals for response rates with the following sample SAS code:

PROC FREQ DATA =;

BY visit;

TABLES trtan*resp / riskdiff;

RUN;

From above code, we can get confidence interval for difference of proportion in PASI90 response between cohorts and also Confidence interval for proportion of PASI90 for individual cohort.

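### The covariate-adjusted PASI 90 result is planned as an odds ratio with no pre-specified link to the 12-point margin that decides the claim

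*SAP*

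**What the plan says.** **Decision rule.** SAP 2.5.2 and Protocol 9.4.2 set the hypotheses on the difference in PASI 90 proportions, Cw6-positive minus Cw6-negative. The claim is made if the upper 97.5% bound of that difference "is less than the non-inferiority margin of 12" per cent (SAP 2.5.2, Interpretation). The sample code in SAP 5.4.1 obtains the difference from PROC FREQ with the `riskdiff` option, without covariates.

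**Adjusted analysis.** SAP 2.5.2 continues: "A logistic regression analysis model will also be fitted, considering age, geographical region", then BMI class, waist, smoking, metabolic syndrome, previous therapy, PsA, age at diagnosis, TNFα-308 and baseline IGA. It names no effect measure for this model, and the interpretation rule does not mention it. In SAP 5.4.1 the model's output statement is "LSMEANS trtpn / diff cl exp", which exponentiates a difference in log odds. The exact-logistic fallback for separation outputs exact odds ratios. The NRI analysis of the primary endpoint (SAP 2.5.3) uses logistic regression too.

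**Elsewhere.** A propensity score is built for confounding, but it enters only the mixed model for continuous PASI change (SAP 2.7.2 and 5.4.3). The Cox model adjusts time to PASI 90, not response at week 16.

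**The concern.** All patients receive the same drug, and the compared groups are formed by genotype, not by randomisation. Under Amendment 1 of the protocol, the regulator asked that TNFα polymorphism, smoking, BMI and metabolic syndrome be taken into account because they might affect response. The sponsor's answer was this regression model. A reader will therefore want to know whether the conclusion survives adjustment.

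The plan gives no rule for answering that. The crude result is a difference in percentage points with a 12-point margin; the adjusted result is an odds ratio with no margin. If the two seem to disagree, someone must choose a conversion after the results are known. If they seem to agree, the agreement has no defined meaning.

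**Working it through.** **1. The plan's own figure.** Inputs from SAP section 3: "considering a one-side alpha level of 0.025 and a power of 80" per cent; 80% PASI 90 in the Cw6-positive cohort; margin 12 points; ratio 219:146. The Cw6-negative rate is not stated. I assume 80%, which reproduces the sample size.

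- n(POS) = (1.960 + 0.842)² × [0.80×0.20 + 0.80×0.20×(219/146)] / 0.12² = 7.849 × 0.40 / 0.0144 = 218.02, rounded up to 219. Then n(NEG) = 146 and the total is 365.
- SE = √(0.16/219 + 0.16/146) = 0.0427. Power = Φ(0.12/0.0427 − 1.960) = 80.2%.
- 365/0.90 = 405.6, so 406 enrolled.

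The plan says "365 patients (219 Cw6-POS and 146 Cw6-NEG) are sufficient"; this reproduces, and it rests on an unadjusted risk difference.

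**2. The margin on the odds-ratio scale.** With POS rate p and NEG rate q = p − 0.12, OR = [p/(1−p)] / [q/(1−q)]. The 71% is the overall rate cited in SAP section 3, used here as a lower value for POS; 80% is the planning value; 90% is my assumption.

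| POS | NEG | Odds POS | Odds NEG | OR equal to 12 points |
|---|---|---|---|---|
| 71% | 59% | 2.448 | 1.439 | 1.70 |
| 80% | 68% | 4.000 | 2.125 | 1.88 |
| 90% | 78% | 9.000 | 3.545 | 2.54 |

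Conversely, a fixed OR of 1.88 means 14.5 points at a POS rate of 71%, 12.0 at 80% and 7.3 at 90%. No single odds ratio stands for the margin.

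**3. Adjustment moves the odds ratio even without confounding.** Hold the marginal rates at 80% and 68%, and let the covariates jointly have SD 0, 0.5, 1.0 or 1.5 on the logit scale (assumed). The covariate-conditional odds ratio is then 1.88, 1.94, 2.10 or 2.36. A gap between the crude and adjusted odds ratios is therefore not by itself a sign of imbalance.

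**4. Illustration of what adjustment could reveal.** The documents give no imbalance data, so the inputs here are assumed, and the adjusted difference is taken as the target. A factor 15 points more common in one cohort and worth 10 points of PASI 90 shifts the crude difference by 0.15 × 0.10 = 1.5 points.

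- Shift against the claim, no true difference: Φ((0.12 − 0.015)/0.0427 − 1.960) = 69% power, down from 80%. The result is 68% to 70%, depending on which cohort's rate carries the shift.
- Shift towards the claim, true rates 80% and 68%: the crude difference is 10.5 points, SE = √(0.80×0.20/219 + 0.695×0.305/146) = 0.0467, and Φ(0.015/0.0467 − 1.960) = 5.1%, against 2.5%.
- In the same way, a 2-point shift gives 6.3% and a 4-point shift 13.8%.

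**5. Feasibility of an adjusted difference.** I used a simulation with 219 and 146 patients, ten independent covariates of log-OR 0.25 each, no confounding and 2,000 trials per scenario (all assumed). The standardised risk difference had 84% power against 80% unadjusted, and type I error was 2.7% for both. No larger sample is needed.

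**The case against.** **The odds ratio is not uninformative.** For a given OR, the largest possible risk difference is (√OR − 1)/(√OR + 1). Setting this to 0.12 gives OR = (1.12/0.88)² = 1.62. In a model without cohort interactions, an upper limit below 1.62 implies a standardised difference under 12 points at any baseline rate. A reader might infer that the planned model can neither confirm nor refute the claim; that goes too far. The bound is strict, however. With 80% in both cohorts, a crude OR estimate of 1 has upper limit exp(1.960 × √(1/(219×0.16) + 1/(146×0.16))) = 1.69. What stands is that the plan pre-specifies no direct comparison.

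**The crude difference may be the right target.** The hypotheses concern the two cohorts as they are, and the stated use is whether HLA-Cw6 testing can be dispensed with. For that predictive question, imbalance that accompanies genotype is part of the answer. A reader might infer that the primary test has an inflated type I error; against the hypothesis as written it does not. The rates in step 4 apply only if the adjusted difference is the target.

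**The covariates are open to dispute.** Protocol 1.1 says HLA-C*06 is associated with phenotypic features of psoriasis. Age at diagnosis, PsA and baseline IGA may lie downstream of genotype, so adjusting for them could remove part of the cohort difference. SAP 2.5.2 also lets covariates be dropped if the model does not converge. This objection stands in full and limits how the adjusted result may be read.

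**The model is supportive, and the code is a sample.** Both are true. SAP 2.5.2 names no output, so the odds-ratio reading rests on SAP 5.4.1. But the documents specify no other output, and a supportive analysis should still bear on the question it supports.

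**Conclusion.** The concern holds as a gap in the supportive analysis. The claim is decided on a crude difference between non-randomised cohorts. The only adjusted comparison of week-16 PASI 90 response comes out, per the sample code, as an odds ratio without a pre-specified link to the margin. The margin's equivalent runs from 1.70 to 2.54 over Cw6-positive rates of 71% to 90%, which is too wide for an informal conversion.

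The documents do not support a finding that the primary test is invalid, that the sample size is wrong, or that adjustment would overturn the conclusion. The effect of imbalance on power or false claims is an illustration on assumed inputs, because the documents contain nothing from which to estimate it.

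**What to change.** In SAP 2.5.2 and 5.4.1, from the same logistic model and covariates, pre-specify a supportive output. Predict each patient's PASI 90 probability once as Cw6-positive and once as Cw6-negative, average each set over all patients, and take the difference. Report it with its upper 97.5% limit by delta method or bootstrap, under LOCF and NRI, and read it against 12%. Leave the crude primary test and its decision rule unchanged.

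Add two statements:

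- Some covariates, such as age at diagnosis, PsA and baseline IGA, may be consequences of genotype. The adjusted difference therefore complements the crude one and does not replace it.
- If the exact-logistic fallback is used, the standardised difference is not available. The exact odds ratio is then reported without comparison to the margin.

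The cost is a small standardisation step beyond the planned output statement. No new data, patients or covariates are needed. It should be fixed before the results are known, so that the scale is not chosen afterwards.
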